3.14 Participant Withdrawal from Study

All attempts must be made to determine the date of the last study drug dose and the primary reason for discontinuation of study drug or study participation. The information will be recorded on the appropriate eCRF page. However, these procedures should not interfere with the initiation of any new treatments or therapeutic modalities that the investigator feels are necessary to treat the participant's condition. Following discontinuation of study drug, the participant will be treated in accordance with the investigator's best clinical judgment, irrespective of whether the participant decides to continue participation in the study.

4 SAFETY MANUAL

4.1 Methods and Timing of Safety Assessment

All serious and nonserious AEs which could be related to study procedures (e.g., infection at liver biopsy site, done during screening) will be collected from the time the participant signed the study-specific informed consent until study drug administration. From the time of study drug administration until 30 days or 5 half-lives after the last dose of study drug or study treatment, all nonserious and serious adverse event (SAE) will be collected whether solicited or spontaneously reported by the participant. After 30 days or 5 half-lives following the last dose of study drug or completion of study treatment only spontaneously reported SAEs will be collected (nonserious AEs will not be collected).

AE = adverse event; SAE = serious adverse event

5 COUNTRY-SPECIFIC REQUIREMENTS

5.1 SUSAR Reporting

AbbVie will be responsible for Suspected Unexpected Serious Adverse Reactions (SUSAR) reporting for the IMP in accordance with global and local guidelines and Appendix A of the Investigator Brochure will

serve as the Reference Safety Information (RSI). The RSI in effect at the start of a DSUR reporting period serves as the RSI during the reporting period. For follow-up reports, the RSI in place at the time of occurrence of the 'suspected' Serious Adverse Reaction will be used to assess expectedness.

6 STUDY DRUG

6.1 Treatments Administered

The study drug (atogepant) will be dispensed in the form of tablets at the visits listed in Section 2.1. Participants will be instructed to take study drug at the same time every day with or without food.

Study drug must not be dispensed without contacting the interactive response technology (IRT) system. Study drug may only be dispensed to participants enrolled in the study through the IRT system. At the end of the Treatment Period or at the Premature Discontinuation visit, the site will contact the IRT system to provide visit date information and study drug return information for each kit.

6.2 Packaging and Labeling

Study drug will be supplied in bottles (atogepant).

Each bottle will be labeled as required per country requirements.

The labels must remain affixed to the bottles. All blank spaces should be completed by site staff prior to dispensing to participant.

6.3 Storage and Disposition of Study Drug

Atogepant must be stored at room temperature. If the temperature goes out of the specified range of 2°C to 30°C (36°F to 86°F), the excursion should be reported.

The investigational products are for investigational use only and are to be used only within the context of this study. The study drug supplied for this study must be maintained under adequate security and stored under the conditions specified on the label until dispensed for participant use or destroyed on site as appropriate.

Sites are responsible for maintaining the investigational study drug according to the storage conditions specified on the clinical label and monitoring for temperature excursions with the use of a calibrated continuous temperature monitoring device (for example, chart recorders and/or acceptable calibrated min/max thermometers) or continuous monitoring systems. Specific guidance on appropriate temperature monitoring and temperature excursions reporting requirements will be provided separately.

6.4 Method of Assigning Participants to Treatment Groups

This is a nonrandomized, open-label, single-arm study. All eligible participants will receive the same dosage of study drug for the duration of the study.

At the Screening visit, all participants will be assigned a unique participant number using the IRT. For participants who do not meet the study selection criteria, the site personnel must contact the IRT system and identify the participant as a screen failure.

Participants who are enrolled will retain their participant number assigned at the screening visit throughout the study. Upon receipt of study drug, the site will acknowledge receipt in the IRT system.

Contact information and user guidelines for IRT use will be provided to each site.

6.5 Selection and Timing of Dose for Each Participant

All tablets of atogepant will be dosed once daily. All participants should take all doses of atogepant with or without food around the same time each day.

7 APPENDICES

7.1 EXAMPLES OF PROHIBITED MEDICATIONS

The following medications are prohibited 30 days prior to Screening (unless otherwise indicated) and throughout the study:

- Strong OATP1B1 inhibitors e.g., Gemfibrozil (Lopid™)

	Strong/Moderate CYP3A4 Inducers	Strong/Moderate CYP3A4 Inhibitors
Anti-depressants/ Anti-anxiety	Barbiturates: Amobarbital (Amytal™) Aprobarbital (Alurate™) Butalbital (Fiorinal™, Fioricet™) Butabarbital (Busodium™, Butisol™) Mephobarbital (Mebaral™) Pentobarbital (Nembutal™) Phenobarbital (Luminal™, Solfoton™) Secobarbital (Seconal™)	Nefazodone (Serzone™)
Anti-seizure	Carbamazepine (Atretol™, Carbatrol™, Epitol™, Equetro™, Tegretol™) Oxcarbazepine (Trileptal™) Phenytoin (Dilantin™, Phenytek™) Primidone (Myidone™, Mysoline™)	
Diabetes	Pioglitazone (Actos™) Troglitazone (Rezulin™, Resulin™)	
Antiemetic		Aprepitant (Emend™)
Anti-hypertension		Diltiazem (Cardizem™) Verapamil (Calan™, Calan SR™)
Glucocorticoid (systemic)	Betamethasone (Celestone™) Dexamethasone (Baycadron™, DexPak™) Hydrocortisone (Cortef™) Methylprednisolone (Medrol™) Prednisolone (Prelone™) Prednisone (Deltasone™) Triamcinolone (Kenalog™)	
Antibiotics	Rifabutin (Mycobutin™) Rifampicin/Rifampin (Rifadin™, Rifater™, Rimactane™)	Erythromycin (Benzamycin™, EryTab™) Clarithromycin (Biaxin™) Telithromycin (Ketek™)
Anti-fungal		Fluconazole (Diflucan™, Trican™) Itraconazole (Sporanox™) Ketoconazole (Nizoral™)

	Strong/Moderate CYP3A4 Inducers	Strong/Moderate CYP3A4 Inhibitors
Anti-HIV	Efavirenz (Stocrin™, Sustiva™) Nevirapine (Viramune™)	Indinavir (Crixivan™) Nelfinavir (Viracept™) Ritonavir (Norvir™) Saquinavir (Fortovase™, Invirase™)
Immune Suppressant		Cyclosporine - Oral/IV only (Neoral™, Sandimmune™)
Others	St. John's wort Enzalutamide (Xtandi™) Modafinil (Provigil™) Armodafinil (Nuvigil™)	Buprenorphine (Cizol™, Subutex™, Suboxone™) Quinine

Drugs with narrow therapeutic margins with potential for CYP drug interactions	Warfarin (Coumadin™) Digoxin (Digitek™, Lanoxin™, Digox™) Cisapride (Prepulsid™, Propulsid™) Pimozide (Orap™)
Drugs with demonstrated efficacy for the prevention of migraine	Valproic acid, sodium valproate, divalproex sodium (Depakote™) Amitriptyline (Elavil™) Nortriptyline (Pamelor™) Metoprolol (Lopressor™, Toprol™) Atenolol (Tenormin™) Nadolol (Corgard™) Propranolol (Inderal™) Timolol (Apo-Timol™) Flunarizine (Sibelium™) Candesartan (Atacand™) Lisinopril (Zestril™, Prinivil™) Desvenlafaxine (Pristiq™) Venlafaxine (Effexor™)

1.0 Introduction

This Statistical Analysis Plan (SAP) describes the statistical analyses for atogepant Study M22-418, A Phase 3, Multicenter, 24-Week, Open-Label Study to Evaluate the Safety, Tolerability, and Efficacy of Atogepant When Added to OnabotulinumtoxinA (BOTOX) for the Preventive Treatment of Chronic Migraine (CM).

The SAP will not be updated in case of administrative changes or amendments to the protocol unless the changes impact the analyses.

Unless noted otherwise, all analyses will be performed using SAS Version 9.4 (SAS Institute Inc., Cary, NC 27513) or later.

2.0 Study Objectives and Design

2.1 Study Objectives

To evaluate the safety and tolerability of atogepant when added to BOTOX over 24 weeks in participants with CM.

To prospectively evaluate the responder rates and change from baseline in monthly migraine days when atogepant is added to BOTOX monotherapy in participants with CM.

[figure not shown]
2.2 Study Design Overview

This is a 24-week, Phase 3, open-label, multicenter study to evaluate the safety and tolerability and explore efficacy of atogepant when added to BOTOX in participants with CM. This study will enroll approximately 75 participants from approximately 30 sites in the United States. Participants will receive once-daily atogepant 60 mg from Day 1 to Week 24, along with their concomitant, standard of care BOTOX. Concomitant BOTOX must be administered on Visits 2, 5, and 8.

The screening/baseline period is up to 12 weeks, which will include at least 28 days of eDiary collection of migraine days and headache days at the end of the screening/baseline period. The treatment period will include 7 scheduled clinic visits: Visit 1/Visit 1a

(Screening/Baseline), Visit 2 (Day 1), Visit 3 (Week 4), Visit 4 (Week 8), Visit 5 (Week 12), Visit 6 (Week 16), Visit 7 (Week 20), and Visit 8/Premature Discontinuation (Week 24). There will be a safety follow-up period of 4 weeks that includes 1 remote visit at Visit 9 (Week 28 or 4 weeks post-atogepant treatment for premature discontinuation). The Visit 9 (Follow-up) must be completed for all participants who take at least one dose of study intervention. The schematic of the study is shown in [Figure 1](#).

Figure 1. Study Schematic

Note: Visits 1 and 1a may be on the same day based on timing of the previous and next BOTOX administrations. Visit 1a should occur approximately 28 days prior to the next scheduled BOTOX administration. Screening assessments should be performed at the study visits specified in Protocol Appendix D.

2.3 Treatment Assignment and Blinding

Approximately 75 participants will receive once-daily atogepant 60 mg from Day 1 to Week 24, along with their concomitant BOTOX (155 to 200 units, targeting approximately 50% of participants receiving 155 units). Concomitant BOTOX must be administered on Visits 2, 5, and 8.

2.4 Sample Size Determination

The study was powered empirically to include approximately 75 participants, as 60 participants with 6 months of exposure are required by payers to support the safety of the atogepant\BOTOX combination. An estimated early termination rate of 20% will allow for 60 participants to complete the 6-month study. 75 participants provide 95% probability to detect at least 1 occurrence of an adverse event (AE) with an incidence of $\geq 4\%$. The precision (half width of 95% confidence interval) of the estimate of change from baseline in mean monthly migraine days will be approximately 1.8 assuming an SD of 7.0 with an effective sample size of 60 participants.

3.0 Endpoints

3.1 Primary Endpoints

The primary objective of the study is to assess the safety endpoints (see Section 3.3).

3.2 Efficacy Endpoints

All efficacy endpoints are exploratory. The definitions of the efficacy measures based on the eDiary data can be found in [Appendix B](#).

- Achievement of $\geq 25\%$, $\geq 30\%$, $\geq 50\%$, $\geq 75\%$, and 100% reduction in mean monthly migraine days across Weeks 1 to 12, Weeks 13 to 24, and at each 4-week interval
- Change from baseline in monthly migraine days across Weeks 1 to 12, Weeks 13 to 24, and at each monthly period
- Change from baseline in monthly headache days across Weeks 1 to 12, Weeks 13 to 24, and at each monthly period
- Change from baseline in monthly moderate or severe headache days across Weeks 1 to 12, Weeks 13 to 24, and at each monthly period
- Change from baseline in monthly cumulative hours of headache across Weeks 1 to 12, Weeks 13 to 24, and at each monthly period

- Change from baseline in monthly acute medication use days across Weeks 1 to 12, Weeks 13 to 24, and at each monthly period
- Change from baseline in monthly headache free days across Weeks 1 to 12, Weeks 13 to 24, and at each monthly period
- Change from baseline in monthly complete migraine symptom-free days across Weeks 1 to 12, Weeks 13 to 24, and at each monthly period
- Change from baseline in monthly cardinal migraine symptom-free days across Weeks 1 to 12, Weeks 13 to 24, and at each monthly period
- Achievement of $\geq 25\%$, $\geq 30\%$, $\geq 50\%$, $\geq 75\%$, and 100% reduction in mean monthly complete migraine symptom-free days across Weeks 1 to 12, Weeks 13 to 24, and at each 4-week interval
- Achievement of $\geq 25\%$, $\geq 30\%$, $\geq 50\%$, $\geq 75\%$, and 100% reduction in mean monthly cardinal migraine symptom-free days across Weeks 1 to 12, Weeks 13 to 24, and at each 4-week interval
- Change from baseline in monthly days with an individual non-headache symptom for each of the 5 most common non-headache symptoms (including difficulty with concentration and thinking clearly collected from AIM-D items 10 and 11) and cardinal individual non-headache symptoms across Weeks 1 to 12, Weeks 13 to 24, and at each monthly period
- Change from baseline in monthly Performance of Daily Activities domain score of the AIM-D at each monthly period
- Change from baseline in monthly Physical Impairment domain score of the AIM-D at each monthly period
- Change from baseline in monthly AIM-D total score at each monthly period
- Change from baseline in monthly AIM-D Item 10 score at each monthly period
- Change from baseline in monthly AIM-D Item 11 score at each monthly period
- Change from baseline in the MSQ v2.1 Role Function-Preventive domain score at Weeks 4, 8, 12, 16, 20 and 24
- Change from baseline in the MSQ v2.1 Role Function-Restrictive domain score at Weeks 4, 8, 12, 16, 20 and 24

- Change from baseline in the MSQ v2.1 Emotional Function domain score at Weeks 4, 8, 12, 16, 20 and 24
- Change from baseline in Patient Health Questionnaire (PHQ-9) total score at Weeks 4, 8, 12, 16, 20 and 24
- Change from baseline in percent work time missed, percent impairment while working, percent overall impairment, and percent activity impairment due to migraine at Weeks 4, 8, 12, 16, 20 and 24 as assessed by the Work Productivity and Activity Impairment Questionnaire: Migraine v2.0 (WPAI: MIGRAINE)
- Participants reporting "satisfied" or "extremely satisfied" with study medication for migraine prevention at Weeks 4, 8, 12, 16, 20 and 24 on the Patient Satisfaction with Study Medication (PSSM)
- Participants assessed by Patient Global Impression of Change (PGIC) as "much better" or "very much better" at Weeks 4, 8, 12, 16, 20 and 24
- Change from baseline in Generalized Anxiety Disorder-7 (GAD-7) total score at Weeks 4, 8, 12, 16, 20 and 24
- Change from baseline in PROMIS v2.0 Cognitive Function Abilities Subset 6a score at Weeks 4, 8, 12, 16, 20 and 24

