9.3.2 Main Analysis of Efficacy Endpoints

The migraine day responder status is defined as participants with at least 25%, 30%, 50%, 75%, and 100% reduction compared to baseline in mean monthly migraine days across Weeks 1 to 12, Weeks 13 to 24, and at each monthly period. They will be summarized using descriptive statistics. Achievement of $\geq 25\%$, $\geq 30\%$, $\geq 50\%$, $\geq 75\%$, and 100% reduction in mean monthly complete migraine symptom-free days and cardinal migraine symptom-free days will be analyzed in a similar way as migraine day responder status.

For endpoints collected from eDiary, change from baseline in monthly migraine days, headache days, moderate or severe headache days, cumulative hours of headache, acute medication use days, headache free days, complete migraine symptom-free days, cardinal migraine symptom-free days, days with individual non-headache symptom for each of the 5 most common and cardinal individual non-headache symptoms, Performance of Daily Activities domain score of the AIM-D, Physical Impairment domain score of the AIM-D, AIM-D total score, AIM-D Item 10 score, and AIM-D Item 11 score at each monthly period, they will be analyzed using a mixed-effect model for repeated measures (MMRM), including visit as a categorical fixed effect, and the baseline score, baseline-by-visit interaction as covariates. An unstructured covariance matrix will be used

to model the covariance of within-participant repeated measurements. The Kenward-Roger approximation¹ will be used to estimate the denominator degrees of freedom. The analysis will be performed based on all postbaseline monthly values using only the observed cases without imputation of missing values. The treatment effect across Weeks 1 to 12, Weeks 13-24 and at each monthly will be estimated by the least square (LS) Means, along with their SE and 95% confidence intervals, and the p-value.

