An acute medication use day is defined as any day on which a participant reports, per eDiary, the intake of allowed medication(s) to treat an acute migraine. The allowed medications include the following categories of drugs: triptans, ergots, opioids, analgesics (including acetaminophen), NSAIDs (including aspirin), and antiemetics.

A moderate or severe headache day is defined as a headache day during which the maximum pain intensity is either moderate or severe. Headache day pain intensity is defined as the worst pain intensity on any headache day where headache pain intensity will be subjectively rated by the patient on a scale from mild to severe:

- Mild pain (1)
- Moderate pain (2)
- Severe pain (3)

Moderate/severe headache day is defined as a headache day during which the maximum pain severity is either moderate or severe. Severe headache day is defined as a headache day during which the maximum pain severity is severe.

If participants experience no headache in a day, then the corresponding pain intensity of that day will be set as missing.

A headache free day is defined as any calendar day on which does not meet the definition of a headache day.

A complete migraine symptom-free day is defined as any calendar day on which a participant reports, per eDiary, no headache and no experience of any of the following non-headache symptom(s): Nausea and/or Vomiting, Sensitivity to light, Sensitivity to sound, Dizziness, Neck pain, Tiredness, Mood change, Yawning, Thirst, Cravings, Urinary frequency, and other (Forehead/facial sweating, Abnormal shedding of tears, Nasal congestion, Eyelid swelling, and Runny nose).

A cardinal migraine symptom-free day is defined as any calendar day on which a participant reports, per eDiary, no headache and no experience of any of the following non-headache symptom(s): Nausea and/or Vomiting, Sensitivity to light, and Sensitivity to sound.

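### As written, the exploratory symptom-free-day achievement endpoints run the wrong way: losing symptom-free days meets the thresholds and gaining them does not

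*SAP*

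**What the plan says.** SAP 3.2 sets thresholds of at least 25%, 30%, 50% and 75%, and of 100%, for two symptom-free-day measures. For the complete version the top category is "100% reduction in mean monthly complete migraine symptom-free days across Weeks 1 to 12, Weeks 13 to 24"; for the cardinal version it is "100% reduction in mean monthly cardinal migraine symptom-free days across Weeks 1 to 12, Weeks 13 to 24, and at each 4-week interval".

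SAP 9.3.2 first sets out the migraine-day responder rule, "defined as participants with at least 25%, 30%, 50%, 75%, and 100% reduction compared to baseline in mean monthly migraine days". It then names the two symptom-free-day endpoints, again as a reduction, and states that "complete migraine symptom-free days and cardinal migraine symptom-free days will be analyzed in a similar way as migraine day responder status".

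SAP Appendix B fixes what is being counted: "A complete migraine symptom-free day is defined as any calendar day on which a participant reports, per eDiary, no headache and no experience" of a list of non-headache symptoms. The cardinal version has the same form with a shorter list: nausea or vomiting, and sensitivity to light or to sound.

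The protocol (3.2 and 7.3) defines responders on migraine days only. For symptom-free days it lists only change from baseline. SAP 15.1 declares no departure from the protocol's planned analyses, so it offers no clarification of the added endpoints.

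**The concern.** Fewer migraine days is an improvement, so a percentage reduction is a sensible success rule for them. Symptom-free days are the opposite kind of count. Carrying the same rule across without reversing it makes the thresholds mark deterioration.

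The word appears for both measures and in both the endpoint list and the analysis section, so it is not a single slip. Because the study has one arm and these summaries are descriptive, no comparator or test would draw attention to the direction. At stake is the meaning of every proportion reported for these two endpoints, and their agreement with the mixed-model results for the same measures, where an increase is favourable.

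**Working it through.** **Inputs.** Thresholds, direction and periods come from SAP 3.2. The meaning of a symptom-free day and the 28-day scaling (recorded days / diary days x 28) come from SAP Appendix B. The entry range of 8 to 23 migraine days is protocol 5.1, criterion 7. The documents give no baseline figures for symptom-free days, so the starting values below are assumed examples. The plan states no figure of its own to reproduce.

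**Step 1: apply three rules to the same participants.** Let b be baseline and p post-baseline symptom-free days per 28.

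- As written: (b - p) / b
- Increase: (p - b) / b
- Reduction in days with symptoms: [(28 - b) - (28 - p)] / (28 - b) = (p - b) / (28 - b)

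| b to p | As written | Thresholds met | Increase | Thresholds met | Days with symptoms | Reduction | Thresholds met |
|---|---|---|---|---|---|---|---|
| 10 to 2 | 80% | 25, 30, 50, 75 | -80% | none | 18 to 26 | -44% | none |
| 10 to 20 | -100% | none | 100% | all five | 18 to 8 | 56% | 25, 30, 50 |
| 8 to 4 | 50% | 25, 30, 50 | -50% | none | 20 to 24 | -20% | none |
| 8 to 0 | 100% | all five | -100% | none | 20 to 28 | -40% | none |
| 8 to 12 | -50% | none | 50% | 25, 30, 50 | 20 to 16 | 20% | none |
| 8 to 16 | -100% | none | 100% | all five | 20 to 12 | 40% | 25, 30 |

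Under the written rule, everyone who meets a threshold has worsened. A 100% reduction requires p = 0.

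**Step 2: behaviour in a group (illustration only).** Assume baseline symptom-free days with mean 8 and SD 4 (rounded and limited to 1 to 20), and individual change with SD 5 (result limited to 0 to 28).

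| Mean gain (days) | At least 50% reduction (as written) | At least 50% increase |
|---|---|---|
| 0 | 22.8% | 22.5% |
| 3 | 9.4% | 42.4% |
| 5 | 4.6% | 57.1% |

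The written proportion falls as benefit grows.

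**Step 3: extent.** Six 4-week periods plus two 12-week spans make 8 periods, and 2 x 5 x 8 = 80 proportions.

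**Step 4: why replacing reduction with increase is not enough.** At b = 0 the percentage is undefined. With a 28-day ceiling, an increase of fraction t needs b of at most 28 / (1 + t): 28 / 1.5 = 18.7 days for 50%, 28 / 1.75 = 16 for 75%, and 28 / 2 = 14 for 100%. A migraine day requires a headache, so it cannot be symptom-free. A participant at the lower entry limit can therefore have up to 28 - 8 = 20 symptom-free days, above all three limits. One at the upper limit can have at most 28 - 23 = 5, and possibly 0.

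**Step 5: denominator of the alternative.** By the same logic, 28 - b is about 8 or more for anyone meeting criterion 7. It is approximate because screening diary collection may run slightly longer than the last 28 days used as the analysis baseline.

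**The case against.** The strongest reply concerns consequence, not wording. SAP 3.2 calls all efficacy endpoints exploratory, the primary objective is safety, these proportions are summarized descriptively, and the sample size does not rest on them. The same two measures are analysed as change from baseline by mixed model, with least-squares means and 95% confidence intervals over the same periods, and those results would show the true direction. A table titled with the SAP's own wording would also disclose that it counts losses. All of this stands, and it limits the severity.

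A reader might infer that worsening participants are in fact reported as responders. The documents do not support that. SAP 3.2 speaks of achievement, and the link to responder status comes only through the cross-reference in 9.3.2. Nothing shows how the derivation was programmed. Appendix B also refers, for one derivation, to a separate document that is not available here. Nothing indicates that it corrects this point, but it cannot be ruled out.

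A reader might also take 80 proportions as 80 errors. The thresholds are nested and the 12-week spans overlap the monthly periods, so this is one drafting error repeated.

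On the remedy, the documents do not reveal whether the sponsor meant an increase in symptom-free days or a reduction in days with symptoms. These are different quantities: in the table, 8 to 16 days meets all five thresholds on the first and only two on the second. Nor is the second denominator guaranteed to be non-zero. The mITT definition in SAP 4.0 does not require the entry criteria to be met, and SAP 7.3 anticipates participants enrolled in breach of them.

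**Conclusion.** The definition is wrong as written. For both symptom-free-day achievement endpoints, in SAP 3.2 and again in 9.3.2, the thresholds select participants who lose symptom-free days and exclude those who gain them. The 100% category is the worst possible outcome. This follows from the definitions alone and needs no distributional assumption; the simulated percentages do, and they serve only as illustration.

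Whether any result is misreported depends on the text being programmed literally, which the documents cannot show. If the program already uses the opposite direction, the SAP does not describe the analysis, and the handling of a zero baseline and of the ceiling remains unstated. How often a zero baseline would occur is unknown.

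Severity is moderate. The effect is confined to two exploratory, descriptive endpoints. The safety objective, the migraine-day responder endpoint, the change-from-baseline analyses of symptom-free days and the sample size are unaffected.

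**What to change.** Correct the direction in SAP 3.2 and 9.3.2 together, and check the derivation program against the corrected text.

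- **Preferred:** define both endpoints as a reduction of at least 25%, 30%, 50% or 75%, or of 100%, in monthly days with symptoms (28 minus monthly complete symptom-free days, and likewise for cardinal). The thresholds and the word reduction stay, the direction becomes right, and the baseline denominator is about 8 or more for anyone meeting entry criterion 7. Add a line for the rare mITT participant whose denominator is zero.
- **Alternative, if an increase in symptom-free days was intended:** say so, and state how a baseline of 0 is handled and how participants are treated for whom a threshold is out of reach, such as a 100% increase from a baseline above 14 days.

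The cost is SAP wording and one derived variable. No new data are needed.
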